#### Age and Gender

4) Men and women, ages 18 and older, inclusive

5) Women of childbearing potential (WOCBP) must be using an adequate method of contraception to avoid pregnancy throughout the study and for up to 8 weeks after the study in such a manner that the risk of pregnancy is minimized. See section 9.7 below for details regarding handling of WOCBP subjects.

WOCBP includes any female who has experienced menarche and who has not undergone successful surgical sterilization (hysterectomy, bilateral tubal ligation, or bilateral oophorectomy) or is not postmenopausal (defined as amenorrhea  $\geq 12$  consecutive months; or women on hormone replacement therapy with documented serum follicle stimulating hormone level > 35 mIU/mL). Even women who are using oral, implanted, or injectable contraceptive hormones or mechanical products such as an intrauterine device or barrier methods (diaphragm, condoms, spermicides) to prevent pregnancy or practicing abstinence or where the partner is sterile (e.g., vasectomy), should be considered to be of child bearing potential. WOCBP who are taking MMF must in addition use methods of birth control as stipulated in the package insert, namely:

Either intrauterine device, or partner with vasectomy, or one hormone (oral contraceptive pill, transdermal patch, vaginal ring, or progesterone injection or implant) and one barrier method (diaphragm or cervical cap with spermicide, contraceptive sponge, or male or female condom), or two barrier methods as described above.

WOCBP must have a negative serum pregnancy test (minimum sensitivity 25 IU/L or equivalent units of human chorionic gonadotropin [HCG]) within 72 hours prior to the start of study medication then every 3 months during the period of study participation.

6) Men must use an adequate method of contraception throughout the study, and for up to 8 weeks after the last infusion, so that the risk of pregnancy to their partners is minimized.

7) MMF must be dosed at 500 mg by mouth twice daily or greater at the time of study entry

8) Prednisone must be dosed at >=10 mg by mouth daily for patients less than 6 weeks posttransplantation, and at >=5mg by mouth daily for patients greater than 6 weeks posttransplantation at the time of study entry.

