6.2.6.2 Mycophenolate Mofetil

All subjects in this study will be treated with MMF. Daily MMF should be administered in 2 divided doses on a consistent schedule in relation to time of day and meals.

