#### Precautions

WOCBP should be advised against becoming pregnant from the beginning of the study until 8 weeks or 5 half lives (whichever is greater) after administration of the last dose.

Subjects should be instructed to contact the Investigator immediately if pregnancy is suspected (e.g., missed or late menstrual period). Male subjects should be advised to avoid unprotected sex throughout the study and until sperm produced during the period of drug exposure has been cleared. Drug-exposed sperm may be present in the semen for 3 months following the passage of 5 half lives of the study drug.

Subjects should be advised to notify the Investigator of any change in birth control method during exposure to Study Drug or if they need to take any prescription drug or other medication not prescribed by the Investigator. The Investigator should be aware of changes in birth control method so that the use of a study-prohibited contraceptive method is identified.

Hormonal contraceptives could be depressed from drug-drug interactions with the study drug or other concomitant medications. Hormonal contraceptives should not be used to prevent pregnancy until a Drug-Drug Interaction (DDI) study has verified that the pharmacokinetics of the hormone contraception remain at therapeutic levels, and this can be substantiated by appropriate PK studies and the investigator believes that this is appropriate for the subject.

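### Section 5.1 accepts a hormone plus a barrier as contraception, while section 9.7 says hormonal contraceptives should not be used until an interaction study is done, so a woman can meet one rule and breach the other.

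*Combined protocol and SAP*

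**What the plan says.** Section 5.1, criterion 5, opens with a general duty: "Women of childbearing potential (WOCBP) must be using an adequate method of contraception to avoid pregnancy throughout the study". It then adds a second layer: "WOCBP who are taking MMF must in addition use methods of birth control as stipulated in the package insert". Four options follow: an intrauterine device; a partner with a vasectomy; "one hormone (oral contraceptive pill, transdermal patch, vaginal ring, or progesterone injection or implant) and one barrier method"; or two barrier methods. Section 6.2.6.2 fixes who falls under this layer: "All subjects in this study will be treated with MMF".

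Criterion 5 also directs the reader onward: "See section 9.7 below for details regarding handling of WOCBP subjects". In section 9.7, under Precautions, the protocol warns that interactions with study drug or other medication could impair hormonal contraceptives. It continues: "Hormonal contraceptives should not be used to prevent pregnancy until a Drug-Drug Interaction (DDI) study has verified" that hormone levels stay therapeutic. It then adds that "this can be substantiated by appropriate PK studies and the investigator believes that this is appropriate for the subject". The same subsection asks the investigator to watch for contraceptive methods that the study prohibits, but gives no list of them. Section 6.4.1 states that no therapies are prohibited.

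**The concern.** The two sections govern the same women and give different answers about one method. Staff who screen against the list in 5.1 would accept a woman on a pill and a condom. Staff who counsel or monitor under 9.7 would tell the same woman that the hormonal part should not be used. Her eligibility could then be judged differently by different people, and so could her compliance during the study.

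The protocol itself supplies the stakes. Section 7.3.2 describes a potential hazard of mycophenolate products to the fetus. Section 6.2.4 lists pregnancy as a reason to stop study therapy at once, and section 9.2 has it handled as a serious adverse event. Section 9.7 gives a safety reason for its restriction, so it is not a mere formality.

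**Working it through.** No arithmetic applies, because the protocol gives no figure on this point. The check sets the passages side by side and looks for anything that reconciles them.

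1. **Do both rules apply to the same women?** Yes. The option list in 5.1 is for women of childbearing potential taking MMF. Section 6.2.6.2 has every subject on MMF, so the list covers every such woman enrolled. Criterion 5 points to 9.7, and 9.7 points back to 5.1 for the definition.

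2. **Does the protocol foresee women on hormonal methods?** Yes. The definition in 5.1 says that women using hormonal contraceptives still count as being of childbearing potential, and the option list names five hormonal forms.

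3. **What does each section say about one hormone plus one barrier?**

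| | Section 5.1, criterion 5 | Section 9.7, Precautions |
|---|---|---|
| Status | Accepted, one of four options | Hormonal part should not be used |
| Condition | None, beyond pairing with a barrier | Interaction study, pharmacokinetic support and investigator agreement |
| Exception for use with a barrier | Not applicable | None stated |

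4. **Is the 9.7 condition shown to be met?** No. The text and reference list cite no interaction study of belatacept with hormonal contraceptives. The schedule in 7.1, the visit procedures in 7.2 and the laboratory tests in 7.3.4 include no hormone measurement. Investigator judgement does not fill the gap: the text joins it to the study and pharmacokinetic requirements and does not offer it as an alternative.

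5. **Does another section settle it?** No. Exclusion criterion 1 in 5.2 turns on whether a method is acceptable but does not define the term. Section 6.4.1 prohibits nothing, while 9.7 assumes that some contraceptive methods are prohibited.

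6. **Result.** A woman using a hormone and a barrier meets the 5.1 list. Under 9.7 she should not be using the hormone unless three conditions hold, and the protocol does not show that they do.

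7. **Reach.** The trial enrols 20 belatacept subjects of both sexes. Those affected are the women of childbearing potential among them who choose the hormone option. That number lies between 0 and 20 and cannot be narrowed from the documents.

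**The case against.** The strongest defence is that the two sections can be followed together. On that reading, 5.1 sets the MMF requirement and 9.7 adds a study-drug precaution that narrows it. Three of the four options in 5.1 name no hormone and satisfy both sections. The restriction is also conditional and worded as advice, and it leaves room for investigator judgement. A qualifying interaction study may exist in the Investigator Brochure or package insert, which the protocol mentions but does not reproduce. Because criterion 5 refers to 9.7, a careful site would see both texts. Finally, 5.1 always pairs the hormone with a barrier, so no woman following its list relies on a hormone alone.

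Much of this stands as a limit on reach. The conflict concerns one option in four, in a trial of 20, and it would disappear if the condition were shown to be met. It does not remove the problem. If 9.7 narrows the list, then 5.1 names as acceptable a method that the protocol elsewhere advises against, and nothing tells the site that the later text prevails. If the condition has been met elsewhere, the protocol should say so. The cross-reference makes it likelier that a site will notice the conflict but does not resolve it. Pairing with a barrier does not help either, since 9.7 makes no exception for it. Even if the wording in 9.7 came from a template, section 10.1 requires the study to be run as the approved protocol describes.

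**Conclusion.** The concern holds. Sections 5.1 and 9.7 contradict each other on whether a hormonal contraceptive may form part of the required method, and a woman can be eligible under one while departing from the other. This rests on the protocol text alone and on the absence from it of any interaction study or planned hormone measurement. It does not assume that no such study exists anywhere. The effect is limited to women who choose the hormone option, at most 20 and probably far fewer since both sexes are enrolled. It bears on eligibility, counselling and the recording of deviations, and has no bearing on endpoints, sample size or analysis. It should be corrected because it concerns reproductive safety in subjects who all take MMF.

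**What to change.** Reconcile 5.1 and 9.7 so that a single list of acceptable contraceptive methods applies at entry and throughout the study, and have each section refer to that list. The sponsor and investigator must decide which statement stands; this review takes no view on the clinical rule. If the condition in 9.7 is considered met, cite the evidence. If it is not, the list in 5.1 and the restriction in 9.7 must be made to agree. Align two related places at the same time: the undefined notion of an acceptable method in exclusion criterion 1 (5.2), and the mismatch between 6.4.1, which prohibits nothing, and 9.7, which presupposes prohibited methods. The cost is a protocol amendment with matching consent wording and review by the institutional review board. No data collection, sample size or analysis changes.

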#### **Testing Methods and Timing**

#### Methods for Pregnancy Testing

Blood or urine testing is acceptable. Urine pregnancy tests must have a minimum test sensitivity of at least 25 IU/L. Kits measuring either total human chorionic gonadotropin (hCG) or the beta ( $\beta$ ) fraction.

#### Timing of Pregnancy Testing

*Outpatient Trials*: WOCBP should be tested:

• At screening

- Every 3 months during period of study participation
- Whenever pregnancy is suspected

#### **Pregnancy Reporting**

In the event that a WOCBP becomes pregnant during a clinical trial, the implications (on the health of the mother and fetus) of treatment suspension must be reviewed and considered. If it is determined that continued treatment is desirable, the IRB must approve continued treatment and participation.

The investigator must immediately notify BMS of this event and complete and forward a *Pregnancy Surveillance Form* to BMS within 24 hours and in accordance with SAE reporting procedures described in Section 7.2.1. The pregnancy should also be reported to the National Transplant Pregnancy Registry. (U.S.)

Follow-up information regarding the course of the pregnancy, including perinatal and neonatal outcome and, where applicable, offspring information must be reported on the Pregnancy Surveillance Form.

Any pregnancy that occurs in a female partner of a male study participant should be reported to BMS. Information on this pregnancy will be collected on the *Pregnancy Surveillance Form*. If required by local regulations or IRB/IEC requirements, the female partner should be asked to sign a *Medical Information Release Form* to acknowledge agreement for disclosure of information if additional information is requested by BMS. (Some countries may require the acknowledgement prior to the initial report of pregnancy.)

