#### 6.2.4 Discontinuation of Therapy

Study therapy MUST be immediately discontinued for the following reasons:

- Withdrawal of informed consent (subject's decision to withdraw for any reason)
- Any clinical AE, laboratory abnormality, or intercurrent illness which, in the opinion of the investigator, indicates that continued treatment with study therapy is not in the best interest of the subject
- Pregnancy

• Imprisonment or the compulsory detention for treatment of either a psychiatric or physical illness (e.g., infectious disease).

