6.6 Withdrawal of Subjects from Study

All efforts should be made to follow all subjects for the entire duration of the study. Withdrawal of a subject from study medication (Section 6.2.4) does not imply that the subject is withdrawn from the study. Section 7.2.4 details study-related procedures for subjects who discontinue study medication.

Subjects MUST be discontinued from study therapy AND withdrawn from the study for the following reasons:

• Withdrawal of informed consent (subject's decision to withdraw for any reason)

• Any clinical AE, laboratory abnormality, or intercurrent illness which, in the opinion of the investigator, indicates that continued treatment with study therapy and further participation in the study (including obtaining vital status of the subject and allograft) is not in the best interest of the subject

• Termination of the study

• Subjects who become prisoners or become involuntary incarcerated for treatment of either a psychiatric or physical (e.g., infectious disease) illness. For discontinuation of study therapy, see Section 6.2.4.

22

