7.3.1 Study Materials Local laboratory will be used for all testing

#### 7.3.2 Safety Assessments

Safety assessments include AEs, clinically significant changes in vital signs, physical examination, and laboratory test abnormalities. The investigator will determine the severity of each AE as mild, moderate, severe, or very severe. In addition, the investigator will determine the relationship of the AE to the administration of the study drug.

Physical examinations may be performed by a Doctor of Medicine, Doctor of Osteopathy, Physician's Assistant, or Nurse Practitioner.

Urine or serum pregnancy tests will be performed prior to the first dose for all WOCBP. If any female subject becomes pregnant, she will be immediately discontinued from study medication.

In addition, for women who become pregnant while using MMF or within 6 weeks of discontinuing therapy, study personnel or the patient's healthcare practitioner will report the pregnancy to the Mycophenolate Pregnancy Reference Registry ([name]) and will strongly encourage the patient to enroll in the pregnancy registry. The patient will also be apprised of the potential hazard of mycophenolate products to the fetus. The risks and benefits of MMF will be discussed with the patient. In certain situations, the patient and her healthcare practitioner may decide that the maternal benefits outweigh the risks to the fetus.

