#### Pregnancy Tests:

A serum pregnancy test (minimum sensitivity 25 IU/L of ß-HCG) must be performed at a local laboratory for all WOCBP within 72 hours prior to the first dose of study medication (baseline or Day 1). Additional testing will occur at weeks 12 and 24, and week 48 for those continuing in the study.

If a female subject becomes pregnant, she will be discontinued from the study.

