#### Pregnancy Reporting Check List

- Confirm in the pregnancy report if study medication has been discontinued.
- Enter positive pregnancy test results on the Case Report Form.
- Submit a completed *Pregnancy Surveillance Form* to BMS and report the pregnancy to the National Transplant Pregnancy Registry (U.S.)
- Provide clarification or follow-up information that is requested by BMS.

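### The protocol contradicts itself on whether a subject who becomes pregnant must stop study drug, and on whether her scheduled follow-up continues

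*Combined protocol and SAP*

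**What the plan says.** Six sections of the combined protocol and SAP bear on a subject who becomes pregnant.

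- Section 6.2.4: "Study therapy MUST be immediately discontinued for the following reasons". Pregnancy is one of the bullets beneath, with no exception attached.
- Section 7.3.2: "If any female subject becomes pregnant, she will be immediately discontinued from study medication".
- Section 7.3.4, under Pregnancy Tests: "If a female subject becomes pregnant, she will be discontinued from the study".
- Section 9.7, under Pregnancy Reporting: "the implications (on the health of the mother and fetus) of treatment suspension must be reviewed and considered", followed by "If it is determined that continued treatment is desirable, the IRB must approve continued treatment and participation". The check list that follows asks the site to "Confirm in the pregnancy report if study medication has been discontinued".
- Section 6.6: "Withdrawal of a subject from study medication (Section 6.2.4) does not imply that the subject is withdrawn from the study". Its own list is introduced by "Subjects MUST be discontinued from study therapy AND withdrawn from the study for the following reasons" and does not name pregnancy.
- Section 7.2.5: a subject who has had at least one dose and then comes off study drug, whatever the cause, keeps the week 4, 12 and 24 procedures while her consent stands. An extra blood draw is added at the time of stopping unless one of those visits falls within 14 days.

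**The concern.** The protocol plans for this event. It enrols women of childbearing potential, schedules pregnancy tests at weeks 12, 24 and 48, handles pregnancy as an SAE and requires notification within 24 hours. A site with a positive test must act at once, and the instruction it follows depends on which section it opens.

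What is at stake first is exposure of mother and fetus to the study drug. Section 9.7 itself recognises that suspending treatment has implications for both. Second, the same wording determines whether the subject goes on contributing immune samples, including the Month 6 sample on which the primary comparison rests.

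**Working it through.** No figure in the plan needs recomputing. The check is a side-by-side reading.

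| Section | Study drug | Scheduled visits and samples |
|---|---|---|
| 6.2.4 | Stop at once, no exception | Silent |
| 7.3.2 | Stop at once, no exception | Silent |
| 7.3.4 | Stops, because she leaves the study | End |
| 7.2.5 | Applies once drug is stopped | Week 4, 12 and 24 procedures continue, given consent |
| 6.6 | Stopping is distinct from leaving | Stopping drug does not by itself end participation |
| 9.7 | May go on, with IRB approval | May go on, with IRB approval |

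**Study drug.** Sections 6.2.4 and 7.3.2 leave nothing to weigh: pregnancy triggers an immediate stop. Section 9.7 requires the weighing and has an outcome in which treatment goes on. Sections 6.2.4, 7.3.2 and 7.3.4 contain no IRB exception, and the continuation sentence in 9.7 does not mention them. The check list in 9.7 treats discontinuation as something to be established, which fits a reading in which it is not automatic. So there are two positions on drug exposure: a mandatory stop, or possible continuation.

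**Follow-up.** Suppose the drug is stopped. Section 7.3.4 then ends participation, while 7.2.5 continues the week 4, 12 and 24 procedures. Section 6.6 supports 7.2.5 to the extent that stopping drug is not the same as leaving.

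**When it bites.** Section 3.1.3 makes Month 6 the primary time point for the immune assays and Months 1, 3 and 12 secondary; section 4.2 places the primary analysis at 24 weeks. After a positive routine test at week 12, the infusions at months 4 and 5 and the week 24 primary sample are all undetermined. A pregnancy recognised earlier also puts any secondary samples still due in doubt.

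**Size.** The documents give no pregnancy rate, so the count is an assumption. None affected: no effect on the data. One: 1/20 = 5% of the belatacept group, leaving 20 − 1 = 19 subjects at week 24 if sampling ends. Two: 2/20 = 10%, leaving 18.

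**The case against.** The best case for the current text is that its provisions can be read in sequence, or as covering different things.

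- **Stop first, then let the IRB allow a return to treatment.** Section 9.7 speaks of treatment continuing, not resuming, and no restart procedure is given. This does not stand.
- **Section 9.7 is about mycophenolate.** The mycophenolate benefit-risk text is in 7.3.2. Section 9.7 speaks of treatment and participation in the trial, and its check list of study medication, so study treatment is the natural reading.
- **Section 9.7 is generic text.** It is still in force, and section 5.1 sends the reader there for the handling of women of childbearing potential.
- **Section 10.1 governs departures from protocol.** It says how a departure is approved, not which of these sections is the protocol.

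Other objections do stand, and they limit the point. A reader might infer three mutually incompatible rules. That is too strong: leaving the study also stops the drug, so 6.2.4 and 7.3.4 can both be obeyed. A reader might also take the absence of pregnancy from the 6.6 list as forbidding withdrawal. The list is not stated to be exhaustive, and saying that one step does not imply another does not prohibit it. The follow-up conflict therefore rests mainly on 7.3.4 against 7.2.5.

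Nor do the documents support raising the stakes by appeal to mycophenolate, whose use in pregnancy has its own text in 7.3.2. They do not support saying that all follow-up is in doubt either, because 9.7 requires pregnancy-outcome reporting. Only the scheduled study procedures are uncertain.

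**Conclusion.** The contradiction is in the current text and no other section resolves it. It has two parts: immediate stop (6.2.4, 7.3.2) and removal from the study (7.3.4) against possible continuation (9.7); and the end of participation (7.3.4) against continued procedures (7.2.5, with 6.6 in support). It is an internal inconsistency, not a design choice.

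It needs correcting because a mandatory safety stopping rule cannot be followed consistently. The case does not rest on the analysis. Contraception is required, pregnant women are excluded and a negative test is needed before dosing, so the number affected may well be zero. A reader might infer a material threat to the Month 6 comparison, or that the week 12 sample is a primary endpoint. The documents support neither: only week 24 is primary, and the data effect is 5% of the belatacept group per affected subject if sampling ends.

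The conclusion assumes that 9.7 refers to study treatment, which is its natural reading. It takes no view on which clinical rule is right.

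**What to change.** Reconcile sections 6.2.4, 6.6, 7.2.5, 7.3.2, 7.3.4 and 9.7 into two statements and have every section refer to them:

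1. One rule for study drug when pregnancy is confirmed, stating whether any IRB-approved exception exists.
2. One rule for study follow-up, stating whether the scheduled visits and immune samples continue as in 7.2.5, including the week 24 primary sample. Section 7.2.5 stops at week 24, so the rule should also cover week 48 for subjects in the extension.

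While editing, correct the references in 6.6 and 6.6.1 for procedures after stopping study medication. They point to 7.2.4, which describes standard visits; the relevant text is in 7.2.5.

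The sponsor and investigator must choose the rules. The cost is protocol wording and the IRB review that section 10.1 requires for an amendment. No change to sample size, visit schedule or analysis method is needed.
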